7.4 Blinding

This study will be open-label i.e. unblinded to participants and investigators throughout. However, those performing the laboratory assessments will be blinded to treatment allocation in order to reduce bias.

7.5 Emergency Unblinding

Procedures for emergency unblinding are not relevant to this study.

7.6 Baseline data

At visit 1

- Medical history

- Physical examination
- Demographic data
- Vital signs (pulse, blood pressure and temperature) measured supine after 5 minutes' rest
- Weight and BMI
- Concomitant medication
- Lab safety parameters: full blood count, serum urea & electrolytes (sodium, potassium, urea and creatinine), liver function tests, clotting screen; and urinalysis

At visit 2

- Vital signs: pulse, blood pressure and temperature
- Physical examination
- TNF- α , IL-6, serum TXB₂, urine PGI-M, platelet aggregation responses to arachidonic acid, ADP and collagen
- Bleeding time

7.7 Trial assessments

Visit 1 - Screening (Day -21 to 0)

Screening of subjects and all study-related procedures will take place in the Sheffield Clinical Research Facility, a specialist environment for the conduct of clinical research. The following assessments and procedures will be performed:

- Full informed consent, including completion of the informed consent form
- Inclusion/exclusion criteria (see section 6)
- Medical history
- Physical examination
- Demographic data
- Vital signs: pulse, blood pressure and temperature
- Weight and BMI
- Concomitant medication

- Lab safety: 12.5 ml blood sample for full blood count, urea & electrolytes (sodium, potassium, urea and creatinine), liver function tests, clotting screen; and urinalysis

If eligible, subjects will be asked to return to the Clinical Research Facility, Northern General Hospital, on Day 1 for the experimental part of the study. They will be randomised to receive a two-period medication regimen (Figure 3), with each period consisting of 10 to 14 days of aspirin (aspirin lysine) or no aspirin prior to the experimental days, with ticagrelor loading dose at the end of one period, 1 hour prior to endotoxin administration, and without ticagrelor loading dose at the end of the other.

There will be a washout period of at least 5 weeks between the first experimental day and the second medication period. A letter will be sent to the participant's GP to inform them of enrolment in the study. Volunteers who complete the study will receive £100 per medication period/experimental day to reimburse them for their time, inconvenience and any discomfort caused. Transportation to and from the Clinical Research Facility will be provided if necessary. Subjects who fail screening will be recorded on a screen failure log with the reason for failure.

Visit 2 (Day 0)

- Vital signs
- Physical examination
- Reconfirm eligibility criteria met (by a medically qualified member of the study team, see section 6) and no withdrawal criteria met (section 7.10)
- Randomisation
- 27 ml venous blood samples for baseline cytokines, prostanoids, inflammatory markers, platelet function, and plasma, serum, DNA and RNA for storage
- Bleeding time measurement
- Urine sample (around 20 ml will be taken for study purposes) for baseline prostanoid measurement
- Provided with supply of study antiplatelet medication for period 1 as determined by randomisation
- Dosing training for use of aspirin lysine if required

Period 1: Day 1 - Day 10 (to 14)

- Participants will receive one of the following antiplatelet medication regimens for 10 to 14 days:
 - No IMP
 - No aspirin but a loading dose of ticagrelor (180 mg) taken on the last day of the medication period, 1 hour prior to endotoxin injection
 - Aspirin (aspirin lysine) 20 mg BD (only)
 - Aspirin (aspirin lysine) 20 mg BD, and a loading dose of ticagrelor (180 mg) taken on the last day of the medication period, 1 hour prior to endotoxin injection
 - Aspirin (aspirin lysine) 75 mg OD (only)

- Aspirin (aspirin lysine) 75 mg OD, and a loading dose of ticagrelor (180 mg) taken on the last day of the medication period, 1 hour prior to endotoxin injection
- Aspirin (aspirin lysine) 300 mg OD (only)
- Aspirin (aspirin lysine) 300 mg OD, and a loading dose of ticagrelor (180 mg) taken on the last day of the medication period, 1 hour prior to endotoxin injection

Visit 3 - Period 1: Day 11 (to 15)

On arrival

- Vital signs
- Physical examination
- Adverse event recording
- Concomitant medication recorded
- IMP compliance check for period 1
- Medically-qualified member of the research team to confirm that the withdrawal criteria (section 7.10) are not met, prior to proceeding further with visit

-1 hour (1 hour before endotoxin injection)

- IV cannula insertion (x2, one in each arm)
- 35.5 ml venous blood sample for baseline lab safety (full blood count, urea & electrolytes [sodium, potassium, urea and creatinine], liver function tests, clotting screen), cytokines, prostanoids, inflammatory markers and platelet function
- Bleeding time measurement
- Urine sample for prostanoid assessment at baseline
- Receive last dose of aspirin of period 1, or last dose of aspirin plus a loading dose of ticagrelor (180 mg), or no IMP, as directed by randomisation allocation
- Collect unused study medication and perform drug accountability check (sachet/pill count)
- Infusion of 250 ml 0.9% saline over 30 minutes
- 23 ml venous blood at 60 minutes after last dose of oral antiplatelet medication or equivalent time if not receiving IMP during period 1 (just before endotoxin administration)

0 hour (time of endotoxin injection)

- Continuous cardiac monitoring starts
- *E.coli* endotoxin 2 ng/kg intravenously administered over 1 minute
- Vital signs at 5, 15 and 30 minutes post-endotoxin
- Continuous IV infusion of 250 ml 0.9% saline over 1 hour
- 14 ml venous blood sample at 30 minutes post endotoxin

1 hour post endotoxin injection

- Vital signs at 1 hour and 1.5 hours post endotoxin injection
- Continuous IV infusion of 250 ml 0.9% saline over 1 hour
- 14 ml venous blood sample at 1 hour post endotoxin
- Urine sample at 1 hour post endotoxin
- 14 ml venous blood sample at 1½ hours post endotoxin

2 hours post-endotoxin injection

- Vital signs at 2 hours post endotoxin
- Continuous IV infusion of 250 ml 0.9% saline over 1 hour
- 23 ml venous blood sample at 2 hours post endotoxin
- Urine sample at 2 hours post endotoxin

3 hours post-endotoxin injection

- Vital signs at 3 hours post endotoxin
- 23 ml venous blood sample at 3 hours post endotoxin
- Bleeding time measurement at 3 hours post endotoxin

4 hours post-endotoxin injection

- Vital signs at 4 hours post endotoxin
- 14 ml venous blood sample at 4 hours post endotoxin
- Urine sample at 4 hours post endotoxin

6 hours post-endotoxin injection

- Vital signs at 6 hours post endotoxin
- 14 ml venous blood sample at 6 hours post endotoxin
- Urine sample at 6 hours post endotoxin
- Continuous cardiac monitoring ends

Visit 4 (Period 1, 1 day after visit 3)

- Telephone follow-up for adverse events
- Facility to convert to in-person visit if any concerns raised

There will then follow a washout period of at least 5 weeks, and not more than 18 weeks, between the first endotoxin challenge day and the beginning of the second medication period. This is to avoid reliably any tolerance of the response to endotoxin, a phenomenon absent by 5 weeks [39].

Visit 5 (10 to 14 days after visit 3)

- Telephone follow-up for adverse events

Visit 6 (Period 2, Day 0)

- Vital signs (BP, pulse, temperature)
- Physical examination
- Adverse event recording
- Concomitant medication recording
- Medically qualified investigator to confirm eligibility criteria again (see section 6) and that no withdrawal criteria (section 7.10) are met at this point prior to proceeding to medication period 2
- Laboratory safety blood tests: 12.5 ml venous blood for full blood count, urea & electrolytes (sodium, potassium, urea and creatinine), liver function tests, clotting screen
- Medication dispensed for period 2
- Dosing training for use of aspirin lysine if required

Participants will be advised to begin antiplatelet medication, allocated as follows, for period 2 from the morning after visit 6:

- If received no IMP in period 1, to receive no aspirin, but a loading dose of ticagrelor (180 mg) 1 hour before endotoxin injection in period 2.

- If received no aspirin but a loading dose of ticagrelor (180 mg) 1 hour before endotoxin injection in period 1, to receive no IMP in period 2.
- If received aspirin (aspirin lysine) 20 mg BD (only) in period 1, to receive aspirin (aspirin lysine) 20 mg BD plus a loading dose of ticagrelor (180 mg) 1 hour before endotoxin injection in period 2.
- If received aspirin (aspirin lysine) 20 mg BD plus a loading dose of ticagrelor (180 mg) 1 hour before endotoxin injection in period 1, to receive aspirin (aspirin lysine) 20 mg BD (only) in period 2.
- If received aspirin (aspirin lysine) 75 mg OD (only) in period 1, to receive aspirin (aspirin lysine) 75 mg OD plus a loading dose of ticagrelor (180 mg) 1 hour before endotoxin injection in period 2.
- If received aspirin (aspirin lysine) 75 mg OD plus a loading dose of ticagrelor (180 mg) 1 hour before endotoxin injection in period 1, to receive aspirin (aspirin lysine) 75 mg OD (only) in period 2.
- If received aspirin (aspirin lysine) 300 mg OD (only) in period 1, to receive aspirin (aspirin lysine) 300 mg OD plus a loading dose of ticagrelor (180 mg) 1 hour before endotoxin injection in period 2.
- If received aspirin (aspirin lysine) 300 mg OD plus a loading dose of ticagrelor (180 mg) 1 hour before endotoxin injection in period 1, to receive aspirin (aspirin lysine) 300 mg OD (only) in period 2.

Period 2, Days 1 to 10 (to 14)

- Participants take antiplatelet medication for period 2 as determined by the randomisation allocation (figure 3)

Visit 7 (Period 2, Day 11 [to 15])

On arrival

- Vital signs
- Physical examination
- Adverse event recording
- Concomitant medication recorded
- IMP compliance check for period 2
- Medically-qualified member of the research team to confirm that the withdrawal criteria (section 7.10) are not met, prior to proceeding further with visit

-1 hour (1 hour before endotoxin injection)

- IV cannula insertion (x2, one in each arm)
- 35.5 ml venous blood sample for baseline lab safety (full blood count, urea & electrolytes [sodium, potassium, urea and creatinine], liver function tests, clotting screen), cytokines, prostanoids, inflammatory markers and platelet function
- Bleeding time measurement
- Urine sample for prostanoid assessment at baseline
- Receive last dose of aspirin of period 1, or last dose of aspirin plus a loading dose of ticagrelor (180 mg), or no IMP, as directed by randomisation allocation
- Collect unused study medication and perform drug accountability check (sachet/pill count)
- Infusion of 250 ml 0.9% saline over 30 minutes
- 23 ml venous blood at 60 minutes after last dose of oral antiplatelet medication or equivalent time if not receiving IMP during period 1 (just before endotoxin administration)

0 hour (time of endotoxin injection)

- Continuous cardiac monitoring starts
- *E.coli* endotoxin 2 ng/kg intravenously administered over 1 minute
- Vital signs at 5, 15 and 30 minutes post-endotoxin
- Continuous IV infusion of 250 ml 0.9% saline over 1 hour
- 14 ml venous blood sample at 30 minutes post endotoxin

1 hour post-endotoxin injection

- Vital signs at 1 hour and 1.5 hours post endotoxin injection
- Continuous IV infusion of 250 ml 0.9% saline over 1 hour
- 14 ml venous blood sample at 1 hour post endotoxin
- Urine sample at 1 hour post endotoxin
- 14 ml venous blood sample at 1½ hours post endotoxin

2 hours post-endotoxin injection

- Vital signs at 2 hours post endotoxin

- Continuous IV infusion of 250 ml 0.9% saline over 1 hour
- 23 ml venous blood sample at 2 hours post endotoxin
- Urine sample at 2 hours post endotoxin

3 hours post-endotoxin injection

- Vital signs at 3 hours post endotoxin
- 23 ml venous blood sample at 3 hours post endotoxin
- Bleeding time measurement at 3 hours post endotoxin

4 hours post-endotoxin injection

- Vital signs at 4 hours post endotoxin
- 14 ml venous blood sample at 4 hours post endotoxin
- Urine sample at 4 hours post endotoxin

6 hours post-endotoxin injection

- Vital signs at 6 hours post endotoxin
- 14 ml venous blood sample at 6 hours post endotoxin
- Urine sample at 6 hours post endotoxin
- Continuous cardiac monitoring ends

Visit 8 (Period 2, 1 day after visit 6)

- Telephone follow-up for adverse events
- Facility to convert to in-person visit if any concerns raised

Visit 9 (Period 2, 10 to 14 days after visit 6)

- Telephone follow-up for adverse events

Study investigations will be performed at the following time points:*

*Baseline refers to visit 2, and the pre- and post-endotoxin samples are to be taken during both experimental periods.

- **Inflammatory markers and cytokines**
- TNF- α : Baseline, pre-last medication dose, pre-endotoxin and 0.5, 1, 1.5, 2, 3, 4 and 6 hours post-endotoxin
- IL-6: Baseline, pre-last medication dose, pre-endotoxin and 0.5, 1, 1.5, 2, 3, 4 and 6 hours post-endotoxin
- CRP: Baseline, pre-endotoxin and 6 hours post-endotoxin
- **Prostanoids and Leukotrienes**
- Serum TXB₂: Baseline, pre-last medication dose, pre-endotoxin and 0.5, 1, 1.5, 2, 3, 4 and 6 hours post-endotoxin
- Urinary PGI-M: Baseline, pre-endotoxin and 1, 2, 4 and 6 hours post-endotoxin
- Urinary creatinine: Baseline, pre-endotoxin and 1, 2, 4 and 6 hours
- Serum PGE₂: Baseline, pre-endotoxin and 0.5, 1, 1.5, 2, 3, 4 and 6 hours post-endotoxin
- **Leucocyte phenotype and activation status**
- White blood cell count with differential leukocyte count: Baseline, pre-last medication dose, pre-endotoxin and 0.5, 1, 1.5, 2, 3, 4 and 6 hours post-endotoxin
- **Haemostasis**
- Bleeding time: Pre-endotoxin and 3 hours post-endotoxin
- **Platelet function tests**
- Light transmittance aggregometry (agonists: arachidonic acid 0.3 and 1 mmol/l, collagen 4 and 16 mg/ml, and ADP 20 μ mol/l): Baseline, pre-endotoxin and 3 hours post-endotoxin
- **Samples for storage**
- Plasma for storage: Baseline, pre-last medication dose, pre-endotoxin and 0.5, 1, 1.5, 2, 3, 4 and 6 hours post-endotoxin
- Serum for storage: Baseline, pre-last medication dose, pre-endotoxin and 0.5, 1, 1.5, 2, 3, 4 and 6 hours post-endotoxin
- DNA/RNA for storage: Baseline
- Urine for storage: Baseline, pre-endotoxin and 1, 2, 4 and 6 hours post-endotoxin

Details of fluid management

We anticipate that the total fluid load per volunteer will be 1000 ml over the 8 hours of the day at the NGH-CRF (250 ml preload and 750 ml infusion). The volunteers will also receive fluid boluses if required, which would be typically be in the range of 250-500 ml normal saline, given if mean arterial blood pressure is reduced by 20% or more or to maintain a systolic blood pressure over 100 mmHg and/or to relieve symptoms related to hypotension. Under normal circumstances, we would give a maximum of 1000 ml of

0.9% saline over 1 hour and a maximum of 2000 ml of 0.9% saline over the 8 hours of the day at the NGH-CRF.

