7.8 Long term follow-up assessments

Participants will be followed up 10 (to 14) days after the second endotoxin injection day (Period 2, Day 21) by telephone. Any new adverse events will be recorded. Participants will be thanked for their involvement in the study and arrangements made to provide the monetary reimbursement due to them. In the event of a participant remaining uncontactable at the end of the follow up window, we will interrogate the hospital records of the participant to clarify vital status and any evidence of untoward events. Participants will be declared 'lost to follow up' if they are uncontactable 28 days after the second endotoxin injection day. A file note will be made in this instance.

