9.2 Operational definitions for (S)AEs

Adverse events and reactions will be recorded and reported from randomisation to 10 days after visit 3 (first endotoxin injection day), and from visit 6 (start of period 2) to 10 days after visit 7 (second endotoxin injection day). Thus, adverse events occurring in the break between the first and second medication periods, excepting those originating in the 10 days after endotoxin injection, will not be recorded or reported.

All SAEs will be reported to the sponsor within 24 hours of the research team becoming aware of them. This will be using the sponsor's proforma which will be sent by email to a dedicated address provided

specifically for this purpose. A copy will be kept in the trial master file and the AE log will be completed. All SAEs will be reviewed at the regular trial management group meetings.

All other AEs not meeting the criteria for reporting as serious will be recorded in the CRF, with the exception of the following events which will not be reported, as they can be expected as a normal response to endotoxin:

- Abnormal body temperature, excepting if $>39^{\circ}\text{C}$ and $<34^{\circ}\text{C}$, unless this persists at 6 hours post-endotoxin or meets the criteria for reporting as an SAE.
- Change in pulse rate, excepting pulse rates of >140 bpm and <45 bpm or if meeting the criteria for SAE reporting.
- Change (increase or decrease) in systolic or diastolic blood pressure from baseline of <40 mmHg unless meeting the criteria for SAE reporting.
- Self-limiting symptoms wholly due to endotoxaemia, for example fever, rigors, general malaise, nausea, vomiting or headache, at the discretion of the investigator, unless meeting the criteria for SAE reporting.
- Alterations in leukocyte (or subset) counts, platelet count or C-reactive protein unless meeting the criteria for SAE reporting.

The investigators will assess the relatedness of adverse events to the IMPs (aspirin [aspirin lysine], ticagrelor) and NIMP (endotoxin).

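### Protocol 7.7 times the telephone visits 8 and 9 from visit 6, before the second endotoxin day, which conflicts with the visit order and, for visit 9, with sections 7.8, 9.2 and 9.3

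*Protocol*

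**What the plan says.** Protocol section 7.7 lists the period 2 visits in this order:

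- "Visit 6 (Period 2, Day 0"): safety checks and dispensing. Participants are told to begin medication "for period 2 from the morning after visit 6". No endotoxin is given.
- "Visit 7 (Period 2, Day 11 [to 15"]): the second endotoxin day.
- "Visit 8 (Period 2, 1 day after visit 6"): a telephone call for adverse events, which can be converted to an in-person visit.
- "Visit 9 (Period 2, 10 to 14 days after visit 6"): a telephone call for adverse events.

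In period 1 the matching calls are counted from the endotoxin day itself. The first is "Visit 4 (Period 1, 1 day after visit 3"), and visit 5 comes 10 to 14 days after visit 3.

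Three other parts of the protocol bear on the timing:

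- Section 7.8: "Participants will be followed up 10 (to 14) days after the second endotoxin injection day", given as Period 2 Day 21, by telephone.
- Section 9.2, repeated in 9.3: period 2 events are recorded "from visit 6 (start of period 2) to 10 days after visit 7 (second endotoxin injection day").
- Appendix 1: visits 8 and 9 are listed after endotoxin day 2 as telephone calls, with no days given.

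The SAP does not address visit timing.

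**The concern.** Visits 8 and 9 come after the second challenge in number and on the page, and their content is post-challenge safety follow-up. Their stated timing is counted from a visit that precedes the challenge. A CRF window or visit calendar built from the wording of 7.7 would carry the wrong dates.

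What is at stake is safety data collection after the second endotoxin dose. The protocol has no formal data monitoring committee and relies on its own defined procedures for safety monitoring, so those procedures need to be executable as written. Section 13.5 excludes planned deviations and requires accidental ones to be documented. Staff who call the day after visit 7 therefore depart from the written schedule, and staff who follow the schedule make no such call.

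**Working it through.** This is day arithmetic on the protocol's own period 2 calendar. Day n is taken as n days after visit 6, which fits visit 6 being Day 0 and medication starting the next morning.

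**Inputs**

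- Visit 6: Day 0 (7.7).
- Visit 7, second endotoxin: Day 11, 12, 13, 14 or 15 (7.7).
- Visit 8: visit 6 + 1 day (7.7).
- Visit 9: visit 6 + 10 to 14 days (7.7).
- Final call: 10 (to 14) days after the second endotoxin day, Day 21 (7.8).
- Adverse event window: to 10 days after visit 7 (9.2, 9.3).

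**The plan's own figure first.** Section 7.8 gives Day 21. Visit 7 at its earliest, Day 11, plus 10 days is Day 21, so 7.8 is reproduced and is plainly counted from the endotoxin day. Over all permitted days the 7.8 call runs from 11 + 10 = Day 21 to 15 + 14 = Day 29.

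**Visit 8 as written.** 0 + 1 = Day 1. Relative to visit 7 this is 1 − 11 = −10 to 1 − 15 = −14, that is, 10 to 14 days before the injection.

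**Visit 9 as written.** 0 + 10 to 0 + 14 = Day 10 to 14. Relative to visit 7:

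- earliest: 10 − 15 = −5, five days before the injection;
- latest: 14 − 11 = +3, three days after it.

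There are 5 × 5 = 25 combinations of permitted visit 7 and visit 9 days. Visit 9 falls before visit 7 in 15, on the same day in 4 and after it in 6. These are counts of permitted combinations, not probabilities. In three of them (Days 11/12, 12/13 and 13/14) visit 9 happens to land one day after the injection, but nothing in the schedule aims at this.

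**Against 7.8, 9.2 and 9.3.** Both the 7.8 call and the end of the adverse event window lie at least 10 days after visit 7. The latest possible visit 9 is at +3, so it is always at least 10 − 3 = 7 days short.

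**Against period 1.** Visit 4 is at visit 3 + 1 and visit 5 at visit 3 + 10 to 14, both counted from the endotoxin day. Visits 8 and 9 have the same intervals, but a different starting visit. If the period 1 pattern were applied to period 2, visit 8 would be Day 12 to 16 and visit 9 Day 21 to 29; the latter matches the 7.8 range above. This shows only that 7.8, 9.2, 9.3 and the period 1 pattern agree with one another while 7.7 stands apart. It is not a ruling on what the timing should be.

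**Postponement.** Section 7.10.1 allows a medication period to be restarted. If visit 6 keeps its date in that case, the gap from visit 6 to visit 7 widens and visits 8 and 9 as written lie still further from the challenge.

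**The case against.** The strongest reply is that this is a slip that any reader would see through. Visit 8 is numbered and printed after visit 7 and has the same two bullets as visit 4, and Appendix 1 places both calls after endotoxin day 2. The visit 7 text contains other remnants of period 1: it refers to the last aspirin dose of period 1 and to not receiving IMP during period 1. To follow visit 8 literally, staff would have to hold it before visit 7. The study is single-centre, which makes a misreading less likely. All of this stands as an account of how the wording arose and limits the practical risk. It does not make the wording consistent.

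For visit 9 it can also be said that 7.8 gives the same call with an explicit starting point, and that 9.2 and 9.3 agree with it. That stands too: the 10 to 14 day contact is not lost. It does not cover visit 8, because 7.8, 9.2 and 9.3 do not require a next-day call. For the same reason, the direct conflict with those sections concerns visit 9 only.

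A reader might infer three stronger things that the documents do not support:

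- *That the plan certainly has no next-day contact after the second challenge.* Section 8.6 refers to a trial flow chart and 7.7 to Figure 3, and neither is shown. The claim can be made only for the text that is visible.
- *That every second challenge will go without that contact.* This requires staff to read visit 8 literally and ignore the visit order. It is a worst case, not a demonstrated effect.
- *That unequal adverse event collection between periods would bias the comparison of ticagrelor with no ticagrelor.* The cross-period comparisons specified in the protocol and SAP are pharmacodynamic, and no between-treatment test of adverse events is specified. The order of ticagrelor is randomised within each aspirin regimen, so a difference between periods would not systematically favour either condition.

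**Conclusion.** The inconsistency is real and lies in an operative visit rule. As written, visit 8 precedes the second challenge by 10 to 14 days, and visit 9 lies between 5 days before it and 3 days after it. Visit 9 contradicts 7.8 and falls at least 7 days short of the end of the 9.2 and 9.3 window, but 7.8 supplies the contact. Visit 8 contradicts its own position after visit 7 and its period 1 counterpart, and no visible text otherwise times a next-day contact after the second challenge.

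The probable cause is a cross-reference slip. The consequence is confined to safety follow-up after the second challenge; the primary endpoint, power, alpha and the specified analyses are untouched. The conclusion rests on the Day 0 and Day 11 to 15 calendar in 7.7 and, for visit 8, on the flow chart and Figure 3 not giving the timing. It deserves correction because the rule gives wrong contact dates if followed and the correction costs almost nothing.

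**What to change.** Reconcile the timing of visits 8 and 9 in section 7.7 with the visit order, the period 1 pattern (visits 4 and 5), section 7.8 and the adverse event windows in 9.2 and 9.3. Check the flow chart and Figure 3 for the same discrepancy. Carry the reconciled timing into the CRF visit windows, so that the schedule, the follow-up section and the adverse event window agree. The choice of timing is for the investigators and the sponsor.

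The cost is a wording amendment, assessed by the sponsor under section 13.10. Both calls already exist in the schedule, so no visit, staff or procedure is added.
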